14 STATISTICAL CONSIDERATIONS

All descriptive and inferential statistical analyses will be performed using the most recently released and available SAS statistical software, unless otherwise noted. For categorical variables, the number and percent of each category within a parameter will be calculated for non-missing data. For continuous variables, the mean, median, and standard deviation, as well as the minimum and maximum values, will be presented.

Statistical significance will be declared when the two-tailed p-value is found to be less than or equal to 0.05, unless otherwise noted. Missing data will not be imputed unless otherwise stated. All clinical data captured will be provided in data listings.

14.1 General Design

In the Phase 1b portion of the study, subjects received 50, 100, or 150 mg of tesevatinib for 28 days or until the development of unacceptable toxicity, noncompliance, withdrawal of consent by the subject, or investigator decision. After the MTD for daily dosing had been established according to criteria in the protocol (100 mg QD), 24 additional subjects were enrolled in the Phase 2a portion of the study and treated using two alternative dosing schedules of 150 mg of tesevatinib on Monday, Wednesday, and Friday of each week and 150 mg on Monday and Thursday of each week. While the MTD dose of 100 mg/day was based on criteria defined in the protocol, the occurrence of moderate QTc prolongation in 2 subjects dosed at that level led to a decision to further evaluate the dose of 50 mg/day.

Modeling of ADPKD subpopulations for a randomized Phase 3 clinical study has been performed. Enrollment criteria being considered for Phase 3 are ADPKD subjects with baseline eGFR \geq 35 mL/min/1.73 m² and \leq 80 mL/min/1.73 m², and htTKV \geq 1000 mL. In order to study the safety profile in this specific ADPKD subpopulation, up to 50 additional subjects with PKD and baseline eGFR \geq 35 mL/min/1.73 m2, and \leq 80 mL/min/1.73 m2, and htTKV \geq 1000 mL will be enrolled (SILK Cohort). Each of the up to 50 subjects to be enrolled will be required to complete either PK testing as described for other Phase 2a subjects in this protocol or iothalamate testing. In addition, all 50 subjects will undergo a mandatory 28-day drug holiday after completing the first month of treatment with tesevatinib. During this drug holiday, and 4 weeks after, subjects will return to the clinic weekly for creatinine and tesevatinib plasma

measurements. All subjects will resume tesevatinib treatment at the Month 2 study visit following completion of the 28-day drug holiday.

14.2 Sample Size Justification

Eight subjects per cohort is a standard and reasonable sample size for determination of safety in this Phase 1b portion of the study. Given the frequency and timing of the most common AEs in prior clinical studies of tesevatinib, 8 treated subjects per dose is sufficient to describe the safety profile of tesevatinib in this subject population. These subjects who receive 50 mg daily of tesevatinib will provide 75% likelihood of having at least 1 AE if the true incidence of an AE is 5%.

In the Phase 2a cohort, the 65 subjects in the 50 mg QD dose group will allow an 80% confidence interval of approximately \pm 0.64 mL/min about an expected mean 6-month change from baseline of -2.5 mL/min when the standard deviation is 4.0 mL/min.

14.3 Statistical Considerations

14.3.1 Study Populations

Adult subjects with ADPKD will be enrolled. The safety population will consist of all subjects who receive at least 1 dose of tesevatinib. An evaluable subject will be defined as one who has completed 28 days (for subjects in the Phase 2a portion of the study this will be 25 or 26 days in the Monday/Thursday and Monday/Wednesday/Friday cohorts, and 28 days in the 50 mg daily dosing cohort). Phase 1b unevaluable subjects (subjects who are not evaluable for toxicity) will be replaced. Subjects who do not complete the study, for whatever reason, will have all available data up until the time of termination related to the reason they were terminated included in the analysis. Completion of the study for subjects enrolled in the Phase 1b portion will be defined as uninterrupted completion of the first 28 days of study drug administration, and completion of the study for subjects entered in the Phase 2a portion of the study will be defined as completion of the Month 6 MRI.

For the Phase 2a cohort, all subjects treated will be included in the analyses based on their available data.

14.3.2 Subject Accountability, Demographics, and Baseline Characteristics

Subject disposition will be tabulated by dose cohort. Similarly, subject demographic information and baseline characteristics including PKD traits will be displayed by treatment. Any discrepancy between treatment assigned and treatment received will be accounted for in these displays. Data for screen failures, pertaining to why they failed to qualify to enroll will also be collected.

Similar analyses will be presented for the Phase 2a cohort.

14.3.3 Tesevatinib Exposure

The amount of tesevatinib administered by visit and overall (total dose) will be tabulated and presented by subject in data listings for all cohorts. In addition, delays and all other alterations in tesevatinib administration will be presented.

14.3.4 Concomitant Medications

Concomitant medications will be coded using WHO Drug Dictionary (WHO-DD March 2013, Type B2 or later) and the data will be summarized by dose cohort and presented in tables and listings.

14.3.4.1 Interim Analyses

On Study Day 1, subjects will receive their first daily dose of tesevatinib. During the Phase 1b portion of the study, all subjects within a dosing cohort must complete 28 days of follow-up and the safety data reviewed before subjects from a subsequent dose cohort receive tesevatinib at the next higher dose. Subjects in Cohort 1 will receive the starting dose 50 mg tesevatinib (Dose Level 1). After all subjects in Cohort 1 complete a minimum of 28 days of follow-up and the safety data have been reviewed, dose escalation involving new subjects can begin with Cohort 2 subjects receiving 100 mg tesevatinib daily (Dose Level 2). Similarly, after all subjects in Cohort 2 complete a minimum of 28 days of follow-up and safety data review, dose escalation involving new subjects can precede with Cohort 3 receiving 150 mg tesevatinib daily (Dose Level 3).

14.3.5 Pharmacokinetics

Plasma concentrations of tesevatinib from subjects will be analyzed using validated assays at a central laboratory, and PK parameters will be estimated using standard PK methodology. Plasma

tesevatinib concentrations and PK parameters will be summarized using descriptive statistics. Efforts will be made to identify the specific structure of major tesevatinib metabolites present in all plasma samples collected from 1–24 hours after dosing on Days 1 and 14 in Phase 1b and on Days 1 and 12 (Monday, Wednesday, and Friday dosing) and Days 1 and 25 (Monday and Thursday dosing) in Phase 2a.

14.3.6 Efficacy/Activity

Descriptive statistics, including confidence intervals for GFR, will be presented over time for the Phase 2a cohort. In addition, identical statistics for the change and percent change from baseline GFR over time will be presented with the 6-month change from baseline being of particular interest.

Similar descriptive statistics will be presented for the reciprocal of serum creatinine endpoints.

14.3.7 MRI

Exploratory efficacy analysis will include MRI measurements of kidney volume. htTKV will be calculated using total kidney volume obtained from MRI divided by height in meters. Kidney volume will be determined by MRI at Screening (baseline measurement), and every 6 months thereafter. These results, including change and percent change from baseline, will be summarized descriptively, including confidence intervals. Log transformation may be needed if these data are found not to be normally distributed. A separate set of analyses will be presented for the Phase 2a cohort.

14.3.8 Safety Data

Safety analyses will be performed on all subjects who receive any quantity of study drug. AEs that are unrelated to treatment and that occur more than 30 days after the administration of the last dose of treatment will not be reported or analyzed. Safety evaluation will be performed based on the actual study treatment a subject has received. A separate set of safety analyses will be presented for the Phase 2a cohort.

Safety observations and measurements include AEs, safety laboratory tests, vital sign measurements, physical examinations, pregnancy status, echocardiograms, ECG assessments, and pharmacokinetic data.

Adverse events will be summarized both overall and by dose cohort and tabulated by severity and relationship to tesevatinib (causality). The original terms used by investigators to identify adverse events in the eCRFs will be mapped into preferred terms using MedDRA® (Version 18.1 or higher). Adverse events will then be grouped by MedDRA® preferred terms into frequency tables according to body system. The number and percentage of subjects experiencing adverse events will be tabulated by body system and preferred term both overall and by dose cohort. When an adverse event occurs more than once, the maximum severity and causality will be counted. Additionally, serious adverse events, adverse events that are related to tesevatinib, and adverse events that are unrelated to tesevatinib will be summarized separately. Concurrent illnesses will be listed and examined as possible confounders in the treatment relationship. Finally, any other potentially related adverse events will be analyzed and discussed, as necessary. Concurrent medications/therapies will also be listed.

A listing of all AEs and SAEs by subject will also be provided. The duration of AEs will be determined and included in listings, along with action taken and outcome. Incidence of laboratory abnormalities will be summarized. The worst on-study grade after the first dose of study drug will be summarized. The incidence of NCI-CTCAE Grade ≥ 3 (Version 4.03) laboratory abnormalities under treatment and shifts in toxicity grading from baseline to highest grade post-baseline will be displayed. Results for variables that are not part of the NCI CTCAE (Version 4.03) will be presented in the listings as below, within, and above the normal limits of the local laboratory. Pregnancy test results will be summarized by time point and dose cohort.

Iothalamate testing will be evaluated as data are received to ensure that testing is consistent with no effect on renal function.

Vital sign measurements will be summarized at each scheduled time point using descriptive statistics. Physical examination results will be summarized by scheduled time point. Physical examination results will also be presented in the subject data listings. Physical findings including height and weight will be presented for each subject by visit and dose cohort.

Digital ECG results and wave intervals measurements will be summarized and reported by subject visit and dose cohort and/or as appropriate. QTc(F) prolongation results will be

summarized separately. Covariate analyses will be employed as necessary (eg, QTc[F] interval vs. plasma drug concentration).

Echocardiogram results will be summarized and reported by subject visit and dose cohort and/or as appropriate.

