Duration of Treatment	Subjects will receive study drug for 28 days after the initiation of treatment. After the initial 28-day safety and tolerability assessment period, subjects will, at the investigator's discretion, continue to receive study drug for a total of 24 months from the initiation of treatment. Subjects will be followed for a period of 30 days following the last dose of tesevatinib.
Concomitant Medications	Subjects should avoid ingesting grapefruit, pomelo, or Seville fruit (and juice) with tesevatinib or at any time during the study. Subjects should not take medications that are associated with a risk of QTc(F) interval prolongation and/or torsades de pointes. Additionally, subjects are not permitted to take concomitant medications that inhibit the CYP3A4 isozyme (eg, ketoconazole, itraconazole, erythromycin, clarithromycin) or inducers (eg, dexamethasone, phenytoin, carbamazepine, rifampicin, or phenobarbital). Tesevatinib is also highly protein bound, and other drugs that are also highly protein bound with the exception of warfarin (eg, diazepam, furosemide, dicloxacillin, propranolol, and phenytoin) should be avoided.
	Antiemetics and antidiarrheal medications should not be administered prophylactically before initial treatment with study drug. At the discretion of the investigator, treatment of symptoms with antiemetic and antidiarrheal medications may be undertaken per standard clinical practice.
	Since tesevatinib is a potent inhibitor of MATE transporter proteins, increased levels of concomitant medications that are secreted by the kidney proximal tubule cells into the renal tubule by MATE transporter proteins may occur. Thus, subjects taking cephalexin, cimetidine, dofetilide, fexofenadine, metformin, procainamide, and pyrimethamine should be monitored carefully.
Safety Assessments	Safety assessments will be performed at regular study intervals (refer to Study Assessment table) and include AEs, physical examinations, vital sign measurements, clinical laboratory evaluations (especially renal function), ECGs, echocardiograms, concomitant medication, and pregnancy testing.
	The AE reporting period for a subject enrolled in the study will begin after informed consent through 30 days after the last dose of tesevatinib. Clinical laboratory tests (hematology, chemistry, urinalysis, coagulation,

and thyroid-stimulating hormone [TSH]) will include the following:

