- Evaluate the annualized percent change from baseline in total kidney volume (TKV). TKV will be determined by MRI at Screening (baseline measurement), at the 6-month visit, and every 6 months thereafter.

Statistical Methods

Eight subjects per cohort are standard and a reasonable sample size for determination of safety and tolerability in this Phase 1b/2a study. In the Phase 2a cohort, 24 subjects were enrolled at the MTD using alternative dosing schedules of 150 mg of tesevatinib on Monday, Wednesday, and Friday of each week, or 150 mg of tesevatinib on Monday and Thursday of each week. There were 15 additional subjects in the Phase 2a cohort dosed at 50 mg of tesevatinib daily and up to 50 additional subjects are planned. These subjects who receive 50 mg daily of tesevatinib will provide 75% likelihood of having at least 1 AE if the true incidence of an AE is 5%.

Demographic (eg, gender, age, race) and baseline characteristics (height, weight) will be summarized by dose level and cohort.

Safety analyses will be performed on all subjects who receive any quantity of tesevatinib. Data generated from safety assessments will be presented in listings by subject and summarized by treatment cohort with the Phase 2a cohort being analyzed separately. Treatment-emergent AEs will be summarized using version 18.1 or higher of MedDRA System Organ Class (SOC) and preferred term, classified from verbatim terms. The incidence and percentage of subjects with at least 1 occurrence of a preferred term will be included, according to the most severe intensity. The number of events per preferred term will also be summarized.

Causality (relationship to study treatment) will be summarized separately. ECG (QT/QTc[F]) and PK data will be provided in a prospective statistical plan that will detail the statistical method of analyzing the ECG data and morphological findings.

Efficacy will be explored with regard to the effect of tesevatinib on eGFR. In the Phase 2a cohort, the 65 subjects in the 50 mg QD dose group will allow an 80% confidence interval of approximately \pm 0.64 mL/min about an expected mean 6-month change from baseline of -2.5 mL/min when the standard deviation is 4.0 mL/min. Additional statistical details will be provided in a prospective statistical plan.

Table 4-1: Schedule of Events for Subjects Enrolled in the Safety in Larger Kidneys (SILK) 50 mg Daily Portion of the Study

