13.2 Adverse Event Definition

An adverse event (AE) is defined as any unintended or undesirable, noxious, or pathological change, compared to pre-existing conditions, experienced by a subject during a clinical study or the follow-up period, regardless of relationship to study drug. Adverse events include:

- Suspected adverse drug reactions
- Reactions from drug overdose, abuse, withdrawal, sensitivity, or toxicity
- Significant changes or abnormalities, when compared to baseline, in structure (sign), function (symptom), clinical laboratory results, ECG results, or physiological testing. This includes any worsening of a pre-existing condition temporally associated with the use of study drug
- Pre- or post-treatment complications that occur as a result of protocol-mandated procedures
- Pre-existing events, that increase in intensity/severity or change in nature
- Other medical events, regardless of their relationship to the study drug, such as injury, surgery, accidents, extensions of symptoms, or apparently unrelated illnesses

For the purpose of data collection, all untoward events that occur after informed consent through 30 days after the last dose of tesevatinib must be recorded on eCRFs by the investigational site. This requirement includes AEs from unscheduled as well as scheduled visits.

An AE does not include:

- Medical or surgical procedures (eg, surgery, endoscopy, tooth extraction, transfusion); when the condition that leads to the procedure is an adverse event.
- Pre-existing diseases, or conditions or laboratory abnormalities present or detected prior to the screening visit, those do not worsen.
- Situations where an untoward medical occurrence has not occurred (eg, hospitalization for elective surgery, social, and/or convenience admissions).
- Overdose of either KD019 or a concomitant medication without any signs or symptoms, unless the subject is hospitalized for observation.

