3.1.6.1 Missing start and end dates for AE and concomitant medication (CM)

The assumption will be the worst or most conservative judgment when imputing AE and CM start and end dates. The purpose of imputing a start date is to help define whether the AE/CM started while taking study drug.

For a partial or missing start date:

- If the day is missing, the first day of the month will be imputed. If the missing day is the same as the month of first dose of study drug, then the first dose date will be imputed.
- If the day and month are missing, the first day of January will be imputed. If the year is the same as the first dose date, then the first dose date will be imputed.
- If the day is completely missing, the first dose date will be imputed. If the end date suggests it could have started prior to this, the first day of January of the same year as the end date will be imputed.
- When imputing a start date, the start date will ensure that the new imputed date is sensible, i.e., is prior to the end date of the AE or CM.

For a partial or missing end date:

- If the day is missing, the last day of the month or the last assessment date, whichever is earlier, will be imputed.
- If the day and month are missing, the 31st of December or the last assessment date, whichever is earlier, will be imputed

- If the date is completely missing, there will be a need to look at whether the AE/CM is still ongoing before imputing a date. If the ongoing flag is missing, then it will be assumed that AE is still present, or CM is still being taken (i.e., do not impute a date). If the AE/CM has stopped, then the last assessment date will be imputed.

These data imputations are for categorization purpose only and will not be used in the listings.

If the assessment of the relationship of the AE to tesevatinib is missing, then it will be assumed that the AE is related to tesevatinib and the AE considered as such in the frequency tables of possibly related AEs. No imputation should be done at the data level.

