4 LIST OF TABLES, FIGURES, AND LISTINGS

In all tables, figures and listing, results will be presented by treatment cohorts and overall, unless be otherwise specified.

Table/Listing/Figure	Title
Demographics and Baseline Characteristics	
Tables (14.1.Y.Z)	Table 14.1.1 Screen Failure
	Table 14.1.2 Patient Disposition
	Table 14.1.3 Summary of Demographics and Baseline Characteristics
	Table 14.1.4 Summary of Major Protocol Deviations
	Table 14.1.5 Summary of Medical History
Treatment Exposure and Concomitant Medication	
Tables (14.2.Y.Z)	Table 14.2.1 Summary of Treatment Compliance and Exposure
	Table 14.2.2.a Summary of Prior Medications
	Table 14.2.2.b Summary of Concomitant Medications
Efficacy	
Tables (14.3.Y.Z)	Table 14.3.1 Annualized Change in Estimated Glomerular Filtration Rate
	Table 14.3.2 Annualized Percent Change from Baseline in Height Adjusted Total Kidney Volume
	Table 14.3.3 Annualized Percent Change from Baseline in Reciprocal of Serum Creatinine

	Table 14.3.3.1 Annualized Percent Change from Baseline in Reciprocal of Serum Creatinine for Study 101
Safety	
Tables (14.4.Y.Z)	Table 14.4.1 Summary of AEs
	Table 14.4.1.1 Summary of AEs for Study 101
	[REDACTED]
	Table 14.4.2 Summary of TEAEs
	Table 14.4.2.1 Summary of TEAEs for Study 101
	[REDACTED]
	Table 14.4.3 Summary of TEAEs Related to KD019
	Table 14.4.3.1 Summary of TEAEs Related to KD019 for Study 101
	[REDACTED]
	Table 14.4.4 AEs by Preferred Term and Maximum Severity
	Table 14.4.4.1 AEs by Preferred Term and Maximum Severity for Study 101
	[REDACTED]
	Table 14.4.5 AEs by Preferred Term and Strongest Relationship
	Table 14.4.5.1 AEs by Preferred Term and Strongest Relationship for Study 101
	[REDACTED]
	Table 14.4.6 Summary of Grade ≥ 3 TEAEs by System Organ Class and Preferred Term
	Table 14.4.6.1 Summary of Grade ≥ 3 TEAEs by System Organ Class and Preferred Term for Study 101
	[REDACTED]
	Table 14.4.7 Summary of Grade ≥ 3 TEAEs Related to KD019 by System Organ Class and Preferred Term

	Table 14.4.8 Summary of Serious Adverse Events
	Table 14.4.9 Summary of Serious Adverse Events Related to KD019
	Table 14.4.10 Summary of TEAEs leading to Dose Modification
	Table 14.4.11 Summary of TEAEs Related to KD019 leading to Dose Modification
	Table 14.4.12 Summary of TEAEs leading to Dose Discontinuation
	Table 14.4.13 Summary of TEAEs Related to KD019 leading to Dose Discontinuation
	Table 14.4.14 Summary of Clinical Laboratory: Hematology

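### The maximum-severity and strongest-relationship AE tables are not limited to treatment-emergent events, so pre-dose AEs can enter them, and an unrated one would count as related to tesevatinib

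*Protocol*

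**What the plan says.** **Collection window.** Under Safety Assessments in the Protocol Synopsis, AE reporting "will begin after informed consent through 30 days after the last dose of tesevatinib". Protocol 13.2 agrees: "all untoward events that occur after informed consent through 30 days after the last dose of tesevatinib must be recorded on eCRFs". Protocol 7.2.1 and 9.1 place screening within 28 days before the first dose.

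**Protocol analysis text.** The Synopsis (Statistical Methods) says "Treatment-emergent AEs will be summarized using version 18.1 or higher of MedDRA System Organ Class (SOC) and preferred term", with subject counts by most severe intensity. Protocol 14.3.8 says "Adverse events will be summarized both overall and by dose cohort and tabulated by severity and relationship to tesevatinib (causality", and adds that "serious adverse events, adverse events that are related to tesevatinib, and adverse events that are unrelated to tesevatinib will be summarized separately". Neither sentence in 14.3.8 has a treatment-emergent limit.

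**SAP.** Section 3.8.1 defines TEAEs as events that start or worsen after the first dose. It then promises a tabulation by maximum severity and relationship without saying whether AEs or TEAEs are counted. The table list in Section 4 has "Table 14.4.4 AEs by Preferred Term and Maximum Severity" and "Table 14.4.5 AEs by Preferred Term and Strongest Relationship", each with a Study 101 version (14.4.4.1 and 14.4.5.1). Where an AE has no relationship rating, Section 3.1.6.1 says "then it will be assumed that the AE is related to tesevatinib" and counts it that way in the frequency tables. The rule does not mention when the event began.

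**The concern.** An event that began before the first dose, and did not worsen afterwards, cannot be an effect of the drug. If it sits in a severity or causality table by dose cohort, the table no longer describes what happened on treatment. Two consequences follow.

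- **Tables that do not reconcile.** The severe counts in Table 14.4.4 can differ from Table 14.4.6 (Grade ≥ 3 TEAEs). The related counts in Table 14.4.5 can differ from Table 14.4.3 (related TEAEs). Nothing in the plan tells a reader why.
- **Attribution by default.** A pre-dose AE with a blank relationship would be counted as drug-related in Table 14.4.5, and in Table 14.4.9 if serious.

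Safety is part of the Phase 1b primary objective, and the Phase 1b cohorts are small, so one subject shifts a displayed rate noticeably.

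**Working it through.** The plan states no figure for this point, so there is nothing to reproduce. The main check is a comparison of the texts, followed by a rough sizing.

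**Step 1. Will pre-dose AEs be in the data?** Yes, by design. Recording starts at consent. The screening lists in Protocol 9.3.1, 9.4.1 and 9.5.1 include an AE assessment, and Table 4-1 collects AEs from consent for SILK. The definition in 13.2 covers complications of protocol-mandated procedures before treatment. SAP 3.3 removes screen failures, but not the pre-dose AEs of subjects who go on to be dosed.

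**Step 2. Which set does each place use?**

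| Place | Set |
|---|---|
| Synopsis, by most severe intensity | TEAEs |
| Protocol 14.3.8, severity and causality | AEs, no start limit |
| SAP 3.8.1, maximum severity and relationship | not stated |
| SAP Tables 14.4.4 and 14.4.5 | AEs |
| SAP Tables 14.4.3, 14.4.6, 14.4.7, 14.4.10 to 14.4.13 | TEAEs |
| SAP Tables 14.4.8 and 14.4.9 | SAEs, no start limit |

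In the SAP list AE is not shorthand for TEAE, because Table 14.4.1 summarises AEs and Table 14.4.2 summarises TEAEs. Protocol 14.3.8 limits laboratory grades to values after the first dose and drops unrelated AEs that occur more than 30 days after the last dose, but it sets no front limit for AEs.

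**Step 3. What does the missing-relationship rule do?** A pre-dose AE rated not related stays not related. One with no rating becomes related in the tables. It stays out of Tables 14.4.3 and 14.4.7 unless it worsens after dosing, or unless its day of onset is missing in the month of first dose, in which case SAP 3.1.6.1 sets the onset to the first-dose date.

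**Step 4. Size.**

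- *Effect of one subject on a rate*, 100/n: SILK 100/50 = 2 points; Phase 1b 50 mg cohort 100/9 = 11.1 points; 150 mg daily cohort 100/5 = 20 points. Cohort sizes are from Protocol 5.2.2.2.3, and SILK is taken at its maximum of 50.
- *Largest pre-dose share of the AE window*, 28/(28 + d + 30) for d days on drug: 28/86 = 32.6% at 28 days; 28/788.5 = 3.6% at 24 months (730.5 days). This takes the full 28-day screening period.
- *Unrated pre-dose events.* The documents give no rates, so these are assumptions. Take the 65 subjects at 50 mg daily, a proportion r = 5% to 20% with a pre-dose AE, and a proportion m = 1% to 10% of those unrated. Subjects with a pre-dose AE: 65r = 3.25 to 13. Subjects counted as related by default: 65rm = 0.03 to 1.3. Chance of at least one: 1 − (1 − rm)^65 = 3% to 73%.

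**The case against.** A reader might infer that all the severity, causality and SAE tables rest on events since consent, and that screening events will therefore be reported as tesevatinib toxicity. The documents do not support that. The related, Grade ≥ 3, related Grade ≥ 3, and dose-modification and discontinuation tables are all on TEAEs. Protocol 13.3.5 requires a five-level rating that includes not related, 13.3.6 makes it a mandatory field, and 13.3.10 puts it in the minimum information for an SAE report. Section 15 adds computerised queries. Blanks should be rare, and nothing shows that pre-dose events are more prone to them.

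Three further points are fair.

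- The sentence in SAP 3.8.1 on severity and relationship sits in a paragraph that opens with TEAEs, so the authors may have meant TEAEs throughout. The same paragraph also uses AEs for the SOC and PT counts, so the text does not settle it and the table titles point the other way.
- The missing-relationship rule refers to tables of possibly related AEs. Table 14.4.9 plainly is one. That Table 14.4.5 is one too is a reading, though a natural one for a table of strongest relationship.
- SAEs are reportable from consent whatever their cause, and the Synopsis statistics text does not address SAE tables. Showing all SAEs of dosed subjects is a legitimate choice.

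Nor did these tables drive dose decisions. Escalation was decided by Data Safety Committee review (Protocol 11.2), Phase 1b is complete, and 50 mg daily has been selected. What remains is the unresolved analysis set for two tables and a rule with no exception for pre-dose onset.

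**Conclusion.** The point holds in a limited form. The Synopsis, Protocol 14.3.8 and the SAP do not agree on the event set for severity and causality. Followed as titled, Tables 14.4.4 and 14.4.5 admit pre-dose AEs of subjects later dosed and may not match Tables 14.4.6 and 14.4.3. An unrated pre-dose AE would be labelled related in Table 14.4.5, and in Table 14.4.9 if serious.

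The effect on severity counts depends on how many pre-dose AEs occur, which the documents do not say. It matters most where cohorts are small or subjects leave early. The effect on attribution is probably small: about 0 to 1 subject in 65 under the assumed rates above. This is a correction to the reported safety tables; it does not show that the tolerability conclusions are wrong.

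**What to change.** - In SAP 3.8.1 and the table list, name TEAEs as the basis of Tables 14.4.4 and 14.4.5 and of their Study 101 versions, 14.4.4.1 and 14.4.5.1.
- Align the severity and causality sentence in Protocol 14.3.8 with the Synopsis.
- In SAP 3.1.6.1, limit the missing-relationship rule to events with onset or worsening on or after the first dose.
- Flag pre-dose AEs in Listing 16.2.7.1.
- Keep all SAEs in Table 14.4.8 and show pre-dose SAEs separately, so that none are lost.

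The cost is a few lines of wording and one programming filter. The downside is that pre-dose non-serious AEs leave the severity and causality tables and are seen only in the all-AE summaries (Table 14.4.1 and the overall summary, 14.4.22) and the listing.
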